7.4 Efficacy analysis

For all continuous efficacy endpoints mean change from baseline to end of treatment will be presented with simple 95% confidence interval and a t-test of no change from baseline. This will be done both for absolute and relative change. Due to the relatively small sample size, a non-parametric estimate of the change from baseline to end of treatment for each endpoint will be derived using the one-sample Hodges-Lehmann median estimator with corresponding 95% confidence interval.

As some of the continuous endpoints can be close to or below zero at baseline (e.g., absorption of energy), the relative change of such endpoints should be interpreted with great caution as the analysis can lead to meaningless results.

Responder endpoints will be tabulated with number of subjects and percentages of subject in FAS.

Other categorical endpoints will be tabulated with number of subjects and percentages of observed subjects. For ordinal endpoints change from baseline will also be calculated and tabulated.

For endpoints related to nutritional status and nutritional absorption sensitivity analyses will be made excluding subjects missing more than 20% of the planned

injections prior to the time of analysis. Hence the number of injections leading to exclusion will be one at Week 4, six at Week 24, and 11 at Week 52.

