7.2 SECONDARY ENDPOINTS

Efficacy endpoints related to PS volume

- Relative change from baseline in actual weekly PS volume at Weeks 4, 24 and 52
- Absolute change from baseline in actual weekly PS volume at Weeks 24 and 52
- Subjects who achieve a reduction of at least 1 day per week of PS from baseline at Weeks 24 and 52
- Clinical responders (20% reduction of PS volume from baseline) at Weeks 24 and 52
- Subjects reaching enteral autonomy at Weeks 24 and 52
- Energy reduction in the Parenteral Nutrition (PN) from baseline at Weeks 24 and 52

Efficacy endpoint related to nutritional, fluid (wet weight) and electrolyte absorption

- Absolute change in absorption of energy over MB periods from baseline to Week 48 (applicable to the protocol version 4)
- Relative change in absorption of energy over MB periods from baseline at Week 48
- Change in absorption of macronutrients over MB periods from baseline at Week 48

- Absolute change in absorption of energy over MB periods from baseline at Week 4
- Change in absorption of macronutrients over MB periods from baseline at Week 4
- Changes in urine output and urinary electrolytes (sodium, potassium, calcium and magnesium) over MB periods from baseline at Week 4 and at Week 48

Patient reported outcomes (PRO)

- Changes from baseline in [REDACTED] at Weeks 24 and 52
- Patient Global Impression of Change (PGIC) at Weeks 24 and 52
- Changes from baseline in Patient Global Impression of Treatment Satisfaction (PGI-TS) at Weeks 24 and 52
- Changes from baseline in Patient Global Impression of Satisfaction with PS (PGI-SPS) at Week 24 and 52
- Changes from baseline in Patient Global Impression of PS Impact (PGI-PSI) at Week 24 and 52.

PK/PD related endpoints

- Trough plasma concentration
- Plasma citrulline levels

Safety endpoints (applicable to the protocol version 3)

- AESI
- Clinical chemistry, hematology, hemostasis, ADAs, and urine analysis
- AEs

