9.1 GENERAL CONVENTIONS AND STATISTICAL CONSIDERATIONS

The statistical evaluation of the trial will include descriptive statistics of the primary and secondary endpoints reflecting the exploratory nature of the trial. In addition, simple analyses will be provided for efficacy endpoints and PRO.

Descriptive statistics for continuous variables will include the number of subjects, mean and standard deviation, median, first and third quartiles (Q1-Q3), and minimum and maximum values. All raw data will be presented to the original number of decimal places. Where appropriate, means, medians, and confidence intervals will be presented to 1 more decimal place than in the raw data. Likewise, standard deviations will be presented to 2 more decimal places than in the raw data.

Summary statistics for categorical variables will contain count and percentage. Percentages will be presented to one decimal, except for one hundred percent, which will be presented as 100%. Unless otherwise specified, percentages for baseline summaries will be based on the total number of subjects in the respective analysis set, whereas percentages for post-baseline summaries will be based on the total number of subjects assessed (i.e. with non-missing values) in the respective analysis set as specified in Section 8.

Confidence intervals for means and percentages will be calculated when appropriate and will be 2-sided at the 95% level unless otherwise specified. p -values will be reported to 3 decimal places where applicable; p -values less than 0.001 will be reported as $p < 0.001$.

All data will be listed individually by subject, sorted by Subject Identifier (ID) and date of assessment or start date as applicable. In general, listings will be based on SAS except for eligibility and enrollment information including inclusion/exclusion criteria and informed consent, visit/telephone contact information, demographics, adverse events, and death, which will be based on screened subjects. Listings may include age, sex, indication of whether the subject has qualified for analysis set (e.g., SAS or FAS), or analysis record (e.g. Yes if used in analysis), where applicable. In case of indication for analysis set, listings will be generally sorted by subjects qualifying for SAS first before those not qualifying for SAS amongst screened subjects.

For efficacy parameters, the absolute and relative change from baseline will be derived as follows:

- Absolute change from baseline = $X_i - X_0$

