- Relative change from baseline = $100 * (X_i - X_0) / X_0$

Where X_i = observed/assessed value at a given analysis timepoint, whereas X_0 = observed/assessed value at baseline.

All analyses will be performed using [REDACTED]

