The absorption will be defined as dietary intake minus output from fecal excretion over a 72-hour MB period at a given analysis timepoint. Hence, the absorption of energy will be calculated as energy intake minus energy output data (as collected on MB Results eCRF). Since dietary intake and fecal excretion are to be measured daily, i.e. up to 3 measurements may contribute to absorption calculations, the average over all available daily absorption measurements over the 72-hour period will be used for analysis. In other words, absorption data will be derived by average of all available intake minus average of all available excretion, regardless of whether there is a case in which either energy intake or energy output data are missing in a daily measurement.

Similar derivations will be applied for absorption of each of the other MB parameters, such as macronutrients (fat, carbohydrate, nitrogen, and protein).

Similarly, the wet weight absorption will be calculated as average of all wet weight input (oral solid + drinks) minus average of all wet weight output (only using feces) under assumption of 1mL = 1g for oral fluids.

Descriptive statistics will be produced for analyses of the following endpoints using absolute and relative change from baseline:

- Relative change in absorption of energy and wet weight over the MB period from baseline to Week 48.
- Absolute change in absorption of energy and wet weight over the MB period from baseline to Week 4 (See above for the derivation of absorption of energy).
- Change in absorption of macronutrients (fat, carbohydrate, and protein) over the MB period from baseline to Week 4 and to Week 48 (See above for the derivation of absorption of macronutrients).
- Change in urinary electrolytes (calcium, magnesium, sodium, potassium, urea, and creatinine) over the MB periods from baseline to Week 4 and Week 48. Since urinary electrolytes data are expected to be measured over the 72-hour MB period, the average of all available results will be used for analyses for each MB parameter at a given analysis timepoint.
- Change in urine volume over the MB periods from baseline to Week 4 and Week 48. This analysis will be based on average daily urine volume data derived as per Balance Period Calculations eCRF since the average daily urine volume should be calculated based on investigator's decision on which 48 hours of the 72 hour metabolic balance study collection to be used.

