p-values and Hodges-Lehmann median estimator along with 95% CI will be produced for absolute and relative change from baseline where applicable as defined in the introduction of Section 9.7 for the above analysis timepoints. If a measurement of absorption yields a negative value, such a measurement result will be regarded as invalid and treated as non-evaluable for the relative change analysis. In the analysis dataset, such cases will not be flagged as analysis records since it is considered non-evaluable for the relative change analysis.

The following figures will be provided for energy absorption:

- Line graph using individual observations by timepoint
- Line graph using individual relative change from baseline by timepoint
- Cumulative distribution of change from baseline
- Change from baseline – mean (95%CI) by timepoint
- Relative change from baseline (%) – mean (95%CI) by timepoint

Figures will be repeated for other MB parameters, absorption of wet weight, fat, carbohydrate, and protein.

In addition, the absolute and relative change from baseline in average daily urine volume (derived as per Balance Period Calculations eCRF) will be also summarized for other timepoints. The number of subjects with an increase or decrease from baseline of more than 10% will be tabulated by analysis visit up to Week 52.

Furthermore, the change from baseline in urine sodium will be summarized by descriptive statistics for scheduled time points.

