9.7.4 SENSITIVITY ANALYSIS TO THE EFFICACY ANALYSES

The analyses of the following endpoints related to nutritional status and nutritional absorption will be repeated for sensitivity analyses using a subgroup of subjects in the FAS excluding subjects missing more than 20% of the planned injections prior to the respective visit. Hence, the number of injections leading to exclusion will be 1 at Week 4, 5 at Week 24, and 10 at Week 48. In other words, the subgroup for Week 4 analysis will be composed of subjects in the FAS with at least 4 injections prior to the visit date of Week 4 assuming 4 planned injections prior to Week 4. Similarly, the subgroup for Week 24 analysis will be composed of subjects in the FAS with at least 20 injections prior to the visit date of Week 24, whereas the subgroup for Week 48 analysis will be composed of subjects in the FAS with at least 39 injections prior to the visit date of Week 48.

- Change in absorption of energy and wet weight over the MB period from baseline to Week 4 and Week 48
- Relative change in absorption of energy and wet weight over the MB period from baseline to Week 48
- Change in absorption of macronutrients (fat, carbohydrate, and protein) over the MB period from baseline to Week 4 and to Week 48
- Change in urine output and urinary electrolytes (calcium, magnesium, sodium, potassium, urea, and creatinine) over the MB periods from baseline to Week 4 and Week 48
- Changes from baseline in lean body mass, bone mineral content and fat mass by DEXA scan from baseline to Week 4, Week 24, and Week 48
- Change in body weight from baseline to Week 4, Week 24 and Week 48
- Change in dietary intake of wet weight (oral solid food, oral fluid), energy, macronutrients (fat, carbohydrate, nitrogen, and protein), and electrolytes (sodium, potassium, calcium and magnesium) from baseline to Weeks 4 and 48
- Change in fecal excretion of wet weight (feces), energy, macronutrients (fat, carbohydrate, nitrogen, and protein), and electrolytes (sodium, potassium, calcium and magnesium) from baseline at Weeks 4 and 48

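### SAP 9.7.2.2 drops negative absorption from the relative-change analysis at follow-up as well as at baseline, so subjects who go from positive to negative leave because of their outcome

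*SAP*

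**What the plan says.** SAP 9.7.2.2 defines the quantity: "The absorption will be defined as dietary intake minus output from fecal excretion over a 72-hour MB period". It is computed as average intake minus average excretion over the available days. For negative results the section says that if an assessment "of absorption yields a negative value, such a measurement result will be regarded as invalid and treated as non-evaluable for the relative change analysis", and adds: "In the analysis dataset, such cases will not be flagged as analysis records".

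SAP 9.1 defines relative change as 100 × (Xi − X0)/X0, where Xi is the "observed/assessed value at a given analysis timepoint" and X0 is the baseline value.

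The rule reaches:

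- a listed secondary endpoint in SAP 7.2, "Relative change in absorption of energy over MB periods from baseline at Week 48";
- the wet-weight and macronutrient relative changes that SAP 9.7.2.2 adds;
- the sensitivity repeat in SAP 9.7.4, "Relative change in absorption of energy and wet weight over the MB period from baseline to Week 48".

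SAP 9.7 and 9.7.2.2 attach confidence intervals, p-values and Hodges-Lehmann estimates to these analyses.

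Protocol 7.4 raises the underlying problem only for baseline: "As some of the continuous endpoints can be close to or below zero at baseline (e.g., absorption of energy"). It asks for caution in interpretation and excludes nobody. SAP Section 10, which lists departures from the protocol, does not mention the rule.

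**The concern.** Absorption is intake minus fecal output, so a negative value can be a real result rather than a failed measurement. The SAP itself keeps such values for absolute change. A non-positive baseline is a sound reason to withhold a percent change; a negative follow-up value is not, because it never enters the denominator.

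With no timepoint limit, the rule removes a positive-baseline subject exactly when follow-up absorption falls below zero. Those are the worst outcomes on this scale. The subjects left in the relative-change mean, test and interval are then selected on the result. With nine subjects enrolled, losing one matters to the mean.

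**Working it through.** **1. Sign check with the SAP 9.1 formula (illustrative values)**

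| Baseline | Follow-up | Relative change | Interpretable? |
|---|---|---|---|
| 1000 | −200 | −120% | Yes: a loss, correctly signed |
| 200 | −100 | −150% | Yes |
| −200 | 100 | −150% | No: a gain shown as a loss |
| −200 | −400 | +100% | No: a loss shown as a gain |

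Only the baseline part of the rule has an arithmetic basis.

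**2. Direction.** With X0 > 0, Xi < 0 gives a relative change below −100%, and Xi ≥ 0 gives −100% or more. Every dropped value is lower than every retained one, so dropping can only raise the mean.

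**3. Size when it happens, with no SD assumption.** Let one of n positive-baseline subjects turn negative with relative change r < −100, and let the others average m.

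- Mean with the subject kept: ((n−1)m + r)/n. Mean under the SAP rule: m.
- Rise: (m − r)/n > (m + 100)/n.
- n = 9 (2 + 7 enrolled, SAP Section 2): more than 100/9 = 11.1 points at m = 0, and 120/9 = 13.3 at m = 20.
- n = 8 (expected completers, Protocol 7.2): more than 100/8 = 12.5 points at m = 0, and 120/8 = 15.0 at m = 20.

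Invented example: eight subjects at +10, 12, 15, 18, 20, 22, 25 and 28%, and a ninth at −120%. Under the SAP rule n = 8, mean 18.8%, p < 0.001, Hodges-Lehmann 18.8. With the ninth kept, n = 9, mean 3.3%, p = 0.84, Hodges-Lehmann 17.5.

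**4. How often.** The documents give no means or SDs, so every input here is assumed. Each setting has 20,000 simulated trials of nine subjects. True values are normal with the between-subject SD, and baseline and follow-up each carry an independent normal error with the within-subject SD. Kept means baseline > 0; the SAP rule also requires follow-up ≥ 0. Entries are the share of trials with at least one positive-to-negative subject, and the median trial mean, kept vs SAP rule.

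| Parameter, mean (between/within SD) | No true change | Moderate gain* |
|---|---|---|
| Energy 2000 (2000/1000) kJ/day | 46%; 3.7 vs 18.4% | 29%; differ by 9.4 points |
| Energy 4000 (2000/1000) | 16%; 5.9 vs 8.6% | 8%; differ by 1.4 |
| Energy 6000 (2500/1200) | 8%; 4.5 vs 5.4% | 4%; differ by 0.5 |
| Wet weight 500 (400/250) g/day | 47%; 7.2 vs 21.4% | 19%; 60.0 vs 66.1% |
| Wet weight 800 (500/250) | 28%; 6.7 vs 12.4% | 11%; 40.2 vs 42.9% |
| Wet weight 1500 (500/300) | 3%; 4.7 vs 5.0% | 1%; 20.2 vs 20.3% |

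*Gain of 500 kJ/day or 200 g/day. With a wet-weight gain of 400 g/day the shares are 5%, 3% and 0.2%, and the means differ by at most 1.9 points.

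Over 18 settings (the six rows, each with no gain and two sizes of gain, the larger being 1000 kJ/day or 400 g/day), the two rules disagreed on t-test p < 0.05 in 0.1 to 2.0% of trials. The Hodges-Lehmann estimate moves less: with no change and energy 2000 it is −3.0 vs 5.2%.

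**The case against.** **Reading of the rule.** SAP 9.7.2.2 uses the word measurement for daily values. If only negative days were dropped, the direction would no longer be fixed. For example, baseline days of 600, 500 and −200 with a follow-up mean of 350 give (350 − 300)/300 = +16.7% with all days, but (350 − 550)/550 = −36.4% without the negative day. This reading is weak: the section derives absorption from period averages, and the rule acts on analysis records. The ambiguity is still worth removing.

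**Assumed variability.** The within-subject SD is applied to a 72-hour average; 250 g/day for a three-day mean implies about 433 g/day for a single day if days are independent (250 × √3). Halving the within-subject SD, with an energy gain of 500 kJ/day, cuts the share of affected trials to 9%, 2% and 1%, and the differences to 2.1, 0.2 and 0.1 points. This stands: the frequency is uncertain and may be low. Wet-weight absorption is also not itself listed in SAP 7.2.

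**Transparency.** SAP 9.1 lists all data by subject, SAP 9.7 lists metabolic balance results, and SAP 9.7.2.2 plots each subject's values over time. With nine subjects a reader could find the negative value and recompute. Table counts would show a loss but not whether baseline or follow-up caused it, and listings carry the flag only optionally ("or analysis record (e.g. Yes if used in analysis), where applicable"). This softens the harm but leaves the reported mean, test and interval affected.

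**Weight.** Protocol 7.4 already urges caution with relative change, absolute change is untouched, and SAP 9.7.1 states that there is no primary efficacy endpoint. All of this stands and keeps the point minor.

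**Conclusion.** The concern holds and is minor. As written, the SAP excludes subjects from a listed secondary analysis on the basis of their follow-up result, with no arithmetic need and beyond the baseline problem that the protocol describes. Read on the 72-hour average, the effect on the mean among positive-baseline subjects is always upward, by more than (m + 100)/n points for one lost subject.

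Whether any subject would be lost cannot be told from the documents. The effect is small when absorption is well above zero or the true gain is large, and a changed significance call would be rare under the assumed inputs. Confidence is medium, mainly because the Note to File of 6 December 2022 overrides the SAP (SAP Section 2, Appendix 4) and its text was not available.

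**What to change.** First confirm that the Note to File has not already changed the rule. Then, in SAP 9.7.2.2:

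- Make relative change non-evaluable only when the baseline 72-hour average absorption is at or below zero. Naming the 72-hour average settles the daily-value ambiguity, and including zero covers a division that the present wording leaves undefined.
- Keep negative Week 4 and Week 48 averages when baseline is positive.
- Report, per parameter, the number of subjects excluded and their absolute changes.
- Base interpretation on absolute change, because baselines just above zero leave relative change unstable under either rule.

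A line in SAP Section 10 is optional.

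The cost is one SAP sentence and one analysis flag, plus re-running any interim relative-change tables that used the old rule, so that interim and final outputs agree. Because the trial is open-label with interim looks, the change should be documented and made before the final analysis. The downside is that the relative-change tables and figures may contain some extreme negative values and look less favourable.

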9.7.2.3 ANALYSIS OF SECONDARY ENDPOINTS RELATED TO PRO

The change in [REDACTED] total score and other component scores from baseline to scheduled time point(s) will be summarized by descriptive statistics. The number (%) of subjects with [REDACTED] total score ≤ 5 and > 5 will be also summarized by scheduled timepoint. p -values and Hodges-Lehmann median estimator along with 95% CI will be produced for change in [REDACTED] total score at Week 24 and Week 52 as defined in the introduction of Section 9.7. The [REDACTED] total score and other component scores will be derived as defined in [Appendix 2: Scoring Method FOR \[REDACTED\]](#).

Since PGIC, PGI-TS, PGI-SPS, and PGI-PSI responses have seven or fewer ordered categories, the average or total will not be derived from these measures while treating them as ordinal variables. Hence, PGIC, PGI-TS, PGI-SPS, and PGI-PSI will be described by frequency (%) of each response.

There will be a separate table to summarize the observed and change in PGI-TS, PGI-SPS, and PGI-PSI from baseline to scheduled timepoint(s) by descriptive statistics using mean, SD, ...etc.

Similarly, the observed PGIC v2.0 at scheduled timepoint(s) will be also by descriptive statistics using mean, SD, ...etc.

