	
Safety assessments
 
• Colonoscopy* or colonography• Physical examination• Vital signs• Twelve-lead electrocardiogram• Body weight• Adverse events and AESIs• Concomitant medications• Clinical chemistry (including liver enzymes), hematology, and hemostasis• Anti-apraglutide antibodies and their neutralizing capacity (collectively ADA)• Urinalysis• Pregnancy test 
*Also performed for efficacy assessments

Trial product / intervention:	Apraglutide 2.5 mg or 5 mg SC once weekly
Control intervention (if applicable):	Not Applicable
Number of subjects with rationale:	This trial will enroll approximately 10 subjects. No formal sample size calculation has been performed for this trial. This number of subjects is considered sufficient to provide adequate information about the general safety, tolerability, efficacy, PD, and PK of the compound at this stage of development.
Trial duration:	Approximately 4 weeks of screening/baseline and 52 weeks on treatment, followed by a safety follow-up of 4 weeks (± 1 week).
Trial schedule:	First subject in is planned for approximately May 2021 Last subject in is planned for approximately May 2022 Last subject out is planned for approximately May 2023
Principal Investigator:	[REDACTED]
Trial centers:	Three European sites located in Belgium, Denmark, and France.
Statistical considerations:	Given the exploratory nature of the trial, the statistical evaluation will include mostly descriptive statistics and

Phase II Study of Apraglutide in SBS

	simple analysis contrasting 4 weeks, 24 weeks, 48 weeks, or 52 weeks against baseline or screening as appropriate.
GCP statement:	This trial will be conducted in compliance with the protocol, the current Declaration of Helsinki, International Council for Harmonisation-Good Clinical Practice (R2), as well as all national legal and regulatory requirements.

TRIAL SCHEDULE

Table 1: Schedule of Assessments (SoA)

	Screening	Baseline	Treatment Period												End of trial					
			1	2 ³	3	4	5 ³	6	7	8	9	10 ²⁶	11	12	13	14	15	16 ³	17	18
Visit No. ¹			-4 to -2 (Day -28 to -14)	-1 (Day -7 to -3)	0 (Day 0)	2 (+1)	4	8 ⁴ (±1)	12 (±2)	16 (±2)	20 (±2)	24 (±2)	28 (±2)	32 (±2)	36 (±2)	40 (±2)	44 (±1)	48 (±2)	52 (±2 days)	4 weeks after last dose ±1 week
Week (weeks unless indicated)																				
General																				
Informed consent	X																			
Inclusion and Exclusion criteria	X	X																		
Demographics	X																			

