5.1.9.7 Patient Global Impression of Satisfaction with Parenteral Support (PGI-SPS)

This is a single-item questionnaire assessing the subject's satisfaction with PS over the preceding 7 days. Response options range from -2 to 2, very dissatisfied to very satisfied (Appendix 1, Section 16.1.5). Once approved by the IEC(s) all subjects will complete this questionnaire even if it was not included when they enrolled in the trial.

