5.1.9.8 Patient Global Impression of Parenteral Support Impact (PGI-PSI)

This is a three-item questionnaire assessing the impact of PS on the subject's sleep, daily activities, and QoL. All questions have response options ranging from not at all to extremely (Appendix 1, Section **16.1.4**). Once approved by the IEC(s), all subjects will complete this questionnaire even if it was not included when they enrolled in the trial.

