3.0	03Sep2021	
- Corrected inconsistencies and typos- Minor wording changes for clarification and to remove duplication- Sponsor representative changed- Abbreviations list updated- Synopsis – clarified definition of short bowel syndrome and deled PS definition- Secondary endpoints and Section 5.1.9: PROs: added PGI-PSI, PGI-TS & PGI-SPS, PGIC updated, PGIS removed for subjects enrolled after this amendment- Inclusion criteria 3 updated b) and c) to read ‘...not exceeding 25%’- Inclusion criteria No. 8: Definition of planned surgery amended during the trial period- Exclusion criteria No. 5, 8, 9, 10 & 11: minor wording changes to clarify the criteria- Exclusion criteria 15: deleted criteria defining Gilbert’s disease subjects and subjects with PPN associated liver disease- Removed exclusion criteria No 17: unplanned hospitalizations- Removed exclusion criteria No 18: Changes in systemic corticosteroids- Exclusion criteria footnote 1: Further definition details added- Table 1 – Days added to Weeks -1 to -2 (Day -28 to -14)- Table 1 – Inclusion & Exclusion criteria check removed from Visit 3- Table 1 – Telephone contact time point clarified at Week 0, Day 1(+1 day) to assess fluid overload- Table 1 – row added to include subjects completion of diaries- Table 1 – Order of PROs defined in footnote 2- Table 1 – Footnote added detail regarding ADA sample collection following ISR at discretion of Investigator

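### For PGI-SPS and PGI-PSI, SAP 9.1 read literally divides baseline counts by the whole FAS and later counts by those assessed, so response percentages can rise with no subject changing

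*SAP*

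**What the plan says.** **Introduction of the questionnaires.** Protocol Appendix 6 records under version 3.0, dated 03 Sep 2021: "PROs: added PGI-PSI, PGI-TS & PGI-SPS, PGIC updated, PGIS removed for subjects enrolled after this amendment". The synopsis schedule says "First subject in is planned for approximately May 2021". Protocol 5.1.9.7 provides for subjects already in the trial: "Once approved by the IEC(s) all subjects will complete this questionnaire even if it was not included when they enrolled in the trial". Protocol 5.1.9.8 says the same for PGI-PSI: "all subjects will complete this questionnaire even if it was not included when they enrolled in the trial".

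**Endpoint.** SAP 7.2 lists as a secondary endpoint "Changes from baseline in Patient Global Impression of PS Impact (PGI-PSI) at Week 24 and 52", with a matching entry for PGI-SPS.

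**Display.** SAP 9.7.2.3 treats the items as ordinal and states that "PGI-SPS, and PGI-PSI will be described by frequency (%) of each response". A separate table gives observed values and change from baseline by descriptive statistics. SAP 8 places PRO analyses on the FAS.

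**Denominators.** Under SAP 9.1, unless specified otherwise, "percentages for baseline summaries will be based on the total number of subjects in the respective analysis set", while post-baseline percentages use the subjects assessed with non-missing values. SAP 9.7.2.3 specifies nothing different. Protocol 7.4 bases percentages for categorical endpoints other than responder endpoints on observed subjects, makes no exception for baseline, and also asks for change to be tabulated for ordinal endpoints.

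**Baseline and missing data.** SAP 9.2 takes the last assessment before first treatment as baseline. SAP 9.3 does not, in general, replace missing values.

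**The concern.** A subject first given these questionnaires after starting apraglutide has no baseline under SAP 9.2. On the literal reading of SAP 9.1, that subject is in the baseline denominator with no response, and then in both numerator and denominator from the first completed questionnaire. The baseline column and the Week 24 and Week 52 columns of one table are then not on the same footing.

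The trial has no control arm, so baseline against later visits is the only comparison these tables offer. A reader of the percentages could take a product of the denominator for a change in how subjects feel about parenteral support.

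The SAP met a related problem elsewhere. SAP 10 changes SBS-IF-TI-QOL from change to observed scores because its baseline collection was dropped. It has no entry for PGI-SPS or PGI-PSI, and none for the move away from the protocol's denominator.

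**Working it through.** The plan gives no figure on this point to reproduce, and no formal sample size calculation was made. The check is direct arithmetic on proportions.

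**Inputs**
- Enrolled: 2 + 7 = 9 (SAP 2). A FAS of 9 is an assumption.
- m = subjects with no pre-dose PGI-SPS or PGI-PSI. The documents do not give it and set no upper limit. The range shown is 0 to 4.
- Every subject gives the same answer at every visit, so any movement is artificial.

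**Formulas for one item, all 9 assessed later.** In a given category let a be the number among the 9 − m subjects with a baseline, and b the number among the m without.
- Baseline percentage under SAP 9.1 = a/9
- Later percentage = (a + b)/9
- Artificial rise = b/9

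Summed over categories, b adds to m. The baseline column therefore totals (9 − m)/9, later columns total 100%, and the total rise is m/9.

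| m | Baseline column total | Later column total | Total artificial rise (points) |
|---|---|---|---|
| 0 | 9/9 = 100% | 100% | 0 |
| 1 | 8/9 = 88.9% | 100% | 11.1 |
| 2 | 7/9 = 77.8% | 100% | 22.2 |
| 3 | 6/9 = 66.7% | 100% | 33.3 |
| 4 | 5/9 = 55.6% | 100% | 44.4 |

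**In whole subjects, m = 3.** Suppose 4 of the 6 with a baseline and 2 of the 3 without are in one category.
- SAP 9.1: 4/9 = 44.4% at baseline, 6/9 = 66.7% later, a rise of 2/9 = 22.2 points.
- The remaining categories together: 2/9 = 22.2%, then 3/9 = 33.3%, a rise of 11.1 points. The two rises add to 33.3 = 3/9.
- Assessed subjects as denominator: 4/6 = 66.7% at baseline, 6/9 = 66.7% later. No shift.

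**If only the same 6 are assessed later:** 4/9 = 44.4% becomes 4/6 = 66.7%, purely from the denominator.

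**Why a paired table is also needed.** Keep m = 3, but let none of the 3 without a baseline choose the category. SAP 9.1 shows 4/9 = 44.4% at both times, and the whole 33.3 points falls on the other categories. Assessed denominators show 4/6 = 66.7% and then 4/9 = 44.4%, because different subjects contribute at the two visits. Only subjects with both values give 4/6 = 66.7% twice.

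**Mean-change rows.** SAP 9.1 defines change as the visit value minus the baseline value, so both are needed. These rows are paired already, and only their n falls. The observed means alongside them can still cover different subjects at different visits.

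**The case against.** The case on the other side has five parts.

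1. *The wording may not reach this table.* Baseline summaries in SAP 9.1 could mean tables of baseline characteristics, not the baseline column of a by-visit table. Read with Protocol 7.4, and with no deviation listed in SAP 10, the denominator would be observed subjects at every visit and the mismatch would vanish. This reading is tenable, but SAP 9.1 does not limit itself that way. A programmer following the SAP could reasonably use the full FAS.
2. *Controlling documents are not visible.* The Note to File of 06 Dec 2022 supersedes the SAP and the mock-up tables, and its text is not in the SAP. Table shells are in a separate document. Either could settle the denominator. This stands as a limit on certainty.
3. *Nobody may be affected.* A reader might infer from the May 2021 start date that a known share of subjects lacks a baseline. The documents do not support that. The start date was a plan, no enrolment dates are given, and the relevant cut is first dose before ethics approval, not the version date. Zero is possible.
4. *The change endpoint is already handled.* A reader might infer that the SAP has no rule for these subjects. It has one: SAP 9.2 and 9.3 together leave them out of the change summary, and no on-treatment value can stand in as baseline.
5. *The effect is visible and the trial exploratory.* A baseline column totalling 66.7% can be noticed, PRO data are listed by subject, and SAP 9.7.2.3 names no test for these items. This limits the harm but does not make the columns comparable.

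**Conclusion.** The point holds as a conditional defect in the planned frequency tables. If m of an assumed FAS of 9 lack a pre-dose value and SAP 9.1 is applied as written, the response percentages rise by m/9 in total between baseline and later visits with no subject changing: 11.1 points for m = 1, 33.3 for m = 3, 44.4 for m = 4, and nothing for m = 0. One category's share of that rise depends on what the subjects without a baseline answer, and can be zero.

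A reader might infer that the display flatters apraglutide. It does not do so systematically, because satisfied and dissatisfied responses are inflated by the same mechanism. The paired mean-change results are untouched.

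The conclusion rests on the literal reading of SAP 9.1, on a FAS of 9, and on the Note to File containing no correction. It merits a change because the written rule departs from Protocol 7.4 without being declared and yields non-comparable columns for two secondary endpoints.

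**What to change.** In SAP 9.7.2.3, for PGI-SPS and each PGI-PSI item:
- Use the subjects assessed at that visit as the denominator at every visit, including baseline, in line with Protocol 7.4.
- State how many subjects have a pre-dose value.
- Add shift tables from baseline to Week 24 and from baseline to Week 52, limited to subjects with both values.
- Keep all observed on-treatment responses in the by-visit table. Restricting every display to subjects with a baseline would discard data for little gain.

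Check the Note to File and the table shells first. If different denominators are intended, SAP 10 should declare them as a departure from Protocol 7.4.

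The cost is a few sentences, a footnote and small added tables, with no new data. The downside is a smaller stated n for the paired comparison.
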